8.2.3 Electrocardiograms

ECGs are recorded with a computerized 12-lead ECG device after the participants rested for at least 5 minutes in supine position (small pillow under head allowed). These ECGs are evaluated by the investigator for safety signals. ECGs will be transferred to central reading center for evaluation.

During Part 1 up to study Visit 6 (inclusive), triplicate ECG tracings are to be recorded. These triplicate tracings may be transferred to a central ECG reading center for later QT evaluation. The results of the QT evaluations may be reported separately.

For part 2 single ECGs will be recorded and transferred to a central ECG reading center for evaluation.

The following ECG parameters will be determined and transferred to the database:

• Ventricular rate, PR interval, QRS-duration, QT interval.

The QT interval will also be corrected for the heart rate using QTcB and Fridericia's method, i.e. by dividing the observed QT interval by the cube-root of RR:

$$QTcF = \frac{QT}{\sqrt[3]{RR}}$$

8.2.4 Clinical safety laboratory assessments

See Section 10.2 for the list of clinical laboratory tests to be performed and to the SoA for the timing and frequency.

The investigator must review the laboratory report, document this review, and record any clinically significant changes occurring during the study as an AE. The laboratory reports must be filed with the source documents.

Abnormal laboratory findings associated with the underlying disease are not considered clinically significant unless judged by the investigator to be more severe than expected for the participant's condition.

All laboratory tests with values considered clinically significantly abnormal during participation in the study or within one month after the last dose of study intervention should be repeated until the values return to normal or baseline or are no longer considered clinically significant by the investigator or the medical monitor.

If such values do not return to normal/baseline within a period of time judged reasonable by the investigator, the etiology should be identified, and the sponsor notified.

All protocol-required laboratory tests, as defined in Section 10.2, must be conducted in accordance with the laboratory manual and the SoA.

09 FEB 2023 Page: 53 of 95

If laboratory values from non-protocol specified laboratory tests performed at the institution's local laboratory require a change in participant management or are considered clinically significant by the investigator (e.g. SAE or AE or dose modification), then the results must be recorded.

Clinically relevant changes, especially when resulting in a decision against dose titration, are to be documented as AE, with details on the respective lab results provided in the comment field of the AE page in the eCRF.

In case of clinically relevant abnormal laboratory results, the investigator has the discretion to perform unscheduled repeat laboratory examinations earlier than at the intervals provided in the SoA in Section 1.3. These unscheduled examinations should be processed by the central lab to ascertain that the data will be included in the database. At the investigator's discretion, additional laboratory parameters may be investigated and samples may be processed by the local lab. In case of relevant liver enzyme elevation (see also Section 10.5), the investigator should perform a repeat serum chemistry panel 2 times per week (including serum transaminases [AST and ALT] and serum bilirubin), frequency of retesting can decrease to once a week if laboratory abnormalities decrease and participant is asymptomatic.

Estimation of glomerular filtration rate (eGFR)

eGFR will be calculated using CKD-EPI formula, using the serum creatinine concentration measured at screening (Kidney Disease: Improving Global Outcomes (KDIGO) CKD Work Group 2013). The calculation will be done by the central laboratory. In case of a decrease by \geq 40%, a critical alert will be provided to the investigator, as it may represent a reason for treatment discontinuation, as described in Section 7.1.2.

8.2.5 Pregnancy testing

During the initial treatment phase, both urine and serum ß-hCG pregnancy tests are planned to be conducted in women enrolled in this clinical study. Dip stick urine pregnancy tests allow the investigator to take action while the participant is at site in case of a positive test. Serum pregnancy tests are intended to confirm negative test results with higher reliability than urine tests. Later during the study, urine pregnancy tests do not need to be performed at visits where blood is drawn for a serum pregnancy test.

Pregnancy tests are to be performed in all female study participants, unless anatomically sterile, at all study visits, regardless of age and fertility status. When visit intervals are extended to 8 weeks after completion of 24 weeks of treatment (Visit 12), additional urine pregnancy tests are to be performed four weeks after each visit up to Visit 15, in line with the CTFG contraception guidance (CTFG 2014).

09 FEB 2023 Page: 54 of 95

8.3 Adverse events (AEs), serious adverse events (SAEs) and other safety reporting

The definitions of adverse events (AEs) and serious adverse events (SAEs) can be found in Section 10.3.

AEs will be reported by the participant (or, when appropriate, by a caregiver, surrogate, or the participant's legally authorized representative).

The investigator and any qualified designees are responsible for detecting, documenting, and recording events that meet the definition of an AE or SAE and remain responsible for following up all AEs, considered related to the study intervention or study procedures, or that caused the participant to discontinue the study intervention (see Section 7).

The method of recording, evaluating, and assessing causality of AEs and SAEs and the procedures for completing and transmitting SAE reports are provided in Section 10.3.

8.3.1 Time period and frequency for collecting AE and SAE information

All AEs/SAEs will be collected from the signing of the ICF until 28 days after end-of treatment or until the follow-up visit (whichever comes later) at the time points specified in the SoA (Section 1.3).

All SAEs will be recorded and reported to the sponsor or designee immediately and under no circumstance should this exceed 24 hours of learning of the event, as indicated in Section 10.3.4. The investigator will submit any updated SAE data to the sponsor within 24 hours of it being available.

TEAEs will be defined as those AEs that occurred after first dosing and those existing predose AEs that worsened severity post-dose during the main treatment period until 28 days after the last dose of the study drug.

Investigators are not obligated to actively seek information on AEs or SAEs after conclusion of the study participation / the End-of-Study visit. However, if the investigator learns of any AE/SAE, including a death, at any time after a participant has been discharged from the study, and he/she considers the event to be reasonably related to the study intervention or study participation, the investigator must promptly notify the sponsor.

8.3.2 Method of detecting AEs and SAEs

Care will be taken not to introduce bias when detecting AEs and/or SAEs. Open-ended and non-leading verbal questioning of the participant is the preferred method to inquire about AE occurrences.

09 FEB 2023 Page: 55 of 95

8.3.3 Follow-up of AEs and SAEs

After the initial AE/SAE report, the investigator is required to proactively follow each participant at subsequent visits/contacts. All SAEs, and AEs of special interest (as defined in Section 8.3.6), will be followed until resolution, stabilization, the event is otherwise explained, or the participant is lost to follow-up (as defined in Section 7.3). Further information on follow-up procedures is provided in Section 10.3.

8.3.4 Regulatory reporting requirements for SAEs

- Prompt notification by the investigator to the sponsor of an SAE is essential so that legal obligations and ethical responsibilities towards the safety of participants and the safety of a study intervention under clinical investigation are met.
- The sponsor has a legal responsibility to notify both the local regulatory authority and other regulatory agencies about the safety of a study intervention under clinical investigation. The sponsor will comply with country-specific regulatory requirements relating to safety reporting to the regulatory authority, IRB/IEC, and investigators.
- An investigator who receives an investigator safety report describing an SAE or other specific safety information (e.g. summary or listing of SAEs) from the sponsor will review and then file it along with the Investigator's Brochure and will notify the IRB/IEC, if appropriate according to local requirements.
- For all studies except those using medical devices, investigator safety reports must be prepared for suspected unexpected serious adverse reactions according to local regulatory requirements and sponsor policy and forwarded to investigators as necessary.

8.3.5 Pregnancy

- Details of all pregnancies in female participants and, if indicated, female partners of male participants will be collected after the start of study intervention and until the end-of study visit.
- If a pregnancy is reported, the investigator will record pregnancy information on the appropriate form and submit it to the sponsor within 24 hours after obtaining the necessary signed informed consents from the parents.
- While pregnancy itself is not considered to be an AE or SAE, any pregnancy complication or elective termination of a pregnancy for medical reasons will be reported as an AE or SAE.
- Abnormal pregnancy outcomes (e.g. spontaneous abortion, fetal death, stillbirth, congenital anomalies, ectopic pregnancy) are considered SAEs, and will be reported as such.
- The participant /pregnant female partner will be followed to determine the outcome of the pregnancy. The investigator will collect follow-up information on the participant / pregnant female partner and the neonate and the information will be forwarded to the sponsor.

09 FEB 2023 Page: 56 of 95

• Any post-study pregnancy-related SAE considered reasonably related to the study intervention by the investigator will be reported to the sponsor as described in Section 8.3.4. While the investigator is not obligated to actively seek this information in former study participants /pregnant female partner, he or she may learn of an SAE through spontaneous reporting.

• Any female participant who becomes pregnant while participating in the study will discontinue study intervention.

8.3.6 Adverse events of special interest (AESI)

Adverse events of special interest have to be reported to the sponsor along the timelines set for serious adverse events (even though they may not be classified as serious), i.e. within 24 hours of the investigator's awareness, as described in Section 10.3.4.

Adverse events of special interest are:

- Adverse events suggestive of hepatic injury (please refer to Section 10.5)
- Syncope/loss of consciousness
- Acute kidney injury suggested by 2.0 fold increase in serum creatinine or > 50% decrease in eGFR

8.4 Pharmacokinetics

- Plasma samples will be collected for measurement of plasma concentrations of runcaciguat and its metabolites M1, M6 and M7 as specified in SoA. Instructions for the collection and handling of biological samples will be provided by the sponsor. At visits with pre-dose (trough, before intake of study intervention) sampling, study intervention will be administered at the study center by study personnel and the exact time of study intervention intake on the day before the visit and on the day of the visit and the exact sampling time will be recorded in the eCRF. Ideally the study personnel should contact the participant prior to these visits to remind them not to take the study intervention as usual in the morning at home and to document the exact time of study intervention intake on the days before the visit. For Visit 7, the participants should be advised to take their drug as usual in the morning at home and document the time of drug intake.
- The actual date and time (24-hour clock time) of each sample will be recorded. In addition, the actual date and time of study intervention intake on the day prior to the visit day and the actual date and time of study intervention intake on the visit day will be documented in the eCRF.
- Concentration data will be summarized descriptively. These data are trough (pre-dose) plasma concentrations of runcaciguat by visit at Visits 3-6, and 815. Further details will be specified in the statistical analysis plan.

09 FEB 2023 Page: 57 of 95

• Pharmacokinetic data for runcaciguat collected during the study will be analyzed at the end of study using nonlinear mixed effects models. Mixed effects models, or population type models, describe the relationship between e.g. dose, time and pharmacological observations such as plasma drug concentrations. Both structural and random effects are involved in this relationship. A population PK model may be developed to characterize the PK of runcaciguat over the entire treatment period using individual runcaciguat concentration data. Individual PK parameters of runcaciguat may be calculated. PK/PD models may be developed to relate parameters of clinical safety and efficacy response with runcaciguat plasma concentrations. The details of the analyses will be described in a separate M&S Analysis Plan, and the results will be reported in a separate M&S Report separately from the main clinical study report.

- Drug concentration information that would unmask the study will not be reported to investigative sites or blinded personnel until the study has been unmasked.
- Details about the collection, processing, storage and shipment of samples will be provided separately (e.g. sample handling sheets or laboratory manual).

8.5 Genetics

Genetic analyses may be part of the biomarker investigations in this study. Genetic analyses are primarily done to address altered drug metabolism, in particular genetic variants that may influence runcaciguat exposure and factors predisposing to cardiovascular and/or eye diseases. The exact genetic variant may arise during the clinical program.

Genetic analyses relate to gene variants such as single nucleotide polymorphisms of drug transporters and/or drug metabolizing enzymes including enzymes of the cytochrome P450 system, the Solute Carrier Family or uridine 5'-diphosphate-glucuronosyltransferase. Different variants predispose to altered metabolization of drugs and may result in differences in runcaciguat exposure. Genetic analyses may be pivotal to understanding the pharmacology of runcaciguat and support its safe and efficacious use resulting in an improved benefit/risk ratio.

Genetic factors predisposing to cardiovascular and/or eye disease may be variants which effect oxidative stress and/or the NO pathway. Oxidative stress and a dysfunctional NO pathway are hallmarks of diabetic retinopathy and other (cardio-)vascular diseases. The study drug acts on soluble guanylate cyclase to produce cGMP in the absence of sufficient NO. Therefore, it is conceivable that certain genetic variants encoding components of the NO-cGMP pathway or genetic variants associated with oxidative stress may influence a participants response to treatment with runcaciguat. In addition, genetic variants may influence the course of disease. For example, asymmetric dimethyl arginine inhibits endogenous NO production. Its breakdown is mainly governed by two enzyme isoforms for which several genetic variants exist. Studies have demonstrated that different variants are associated with different asymmetric dimethyl arginine levels and therefore NO and cGMP bioavailability.

The genetic sample may be used to test for individual single nucleotide polymorphisms deemed relevant to better understand observations related to pharmacokinetics, mode-of-action-related and / or safety of runcaciguat and to further investigate pathomechanisms

09 FEB 2023 Page: 58 of 95

deemed relevant to diabetic retinopathy, cardiovascular disease, and associated health problems. Whole genome sequencing is excluded.

8.6 Biomarkers

In this study, genetic as well as non-genetic biomarkers will be investigated.

8.6.1 Laboratory biomarkers

Biomarkers will be evaluated in samples collected before, during and after treatment in order to determine the impact of runcaciguat. These markers fall into the following categories:

- A. Biomarkers which may be related to the mode-of-action of the study drug: e.g. vasoactive agents such as cGMP, Kynurenines or other tryptophan metabolites
- B. Functional markers of the cardiovascular system and cardiometabolic markers: e.g. B-type natriuretic peptide, Kidney Injury Molecule-1, neutrophil gelatinase-associated lipocalin, clusterin, osteopontin, cystatin-C, uromodulin, heart-fatty acid binding protein, markers of inflammation and/or fibrosis, metabolic markers (e.g. adiponectin, apolipoproteins, HbA1c, glucose, (gluco)corticoids), or markers reflecting the oxidative stress status.
- C. **OMICS** / **Untargeted Multiplex Analysis:** A sample may be collected for (untargeted) analysis (e.g. untargeted metabolomics) in order to identify '*de novo*' pharmacodynamic biomarkers, biomarkers which support the understanding of the mode-of-action and/or biomarkers which may indicate disease progression.
- D. Further biomarkers related to the mode of action or the safety of runcaciguat and similar drugs may be examined. The same applies to further biomarkers deemed relevant to NPDR, (cardio)vascular diseases and associated health problems. These investigations may include e.g. diagnostic, safety, PD, monitoring, or potentially predictive biomarkers.

The following sample types will be collected for biomarker analysis:

- Plasma
 PK or safety lab samples (leftovers) may be used for biomarker investigations.
 Generally, plasma is collected for biomarker analysis. Refer to sample handling sheets for further details as some laboratories may request serum for particular tests.
- Serum (optional)
- Whole blood

Timing – The planned time points of sample collection are provided in the SoA in Section 1.3. If deemed necessary, the sampling time points or frequency according to the SoA may be adjusted.

Sample handling and storage – details on the collection, processing, shipment and storage of samples will be provided in separate documents (e.g. sample handling sheets or lab manual).

09 FEB 2023 Page: 59 of 95

Samples may be stored for a maximum of 15 years (or according to local regulations) following the end of the study at a facility selected by the Sponsor to enable further analyses.

Reporting – Biomarker investigations may be reported separately (e.g. in a biomarker evaluation report) except for biomarkers of Category A above, and serum lipoprotein(s).

8.6.2 Ambulatory blood pressure monitoring (ABPM) – only in Part 1

ABPM evaluations were removed from the protocol via Amendment 3.

8.7 Immunogenicity assessments

Not applicable.

8.8 Health economics

Health Economics/Medical Resource Utilization parameters are not evaluated in this study.

9. Statistical considerations

As of amendment 3, this Section and its sub-sections were integrated from Master Protocol. In this section, the following terminology will be used:

- 'Clinical activity' will be used as a synonym for 'superiority of runcaciguat vs placebo'.
- 'Clinical relevance' will be used with its usual meaning (i.e. an effect that is sufficiently high to be of clinical interest).

9.1 Statistical hypotheses

The primary endpoint is the proportion of patients with " \geq 2-step improvement in DRSS at 48 weeks of treatment in the study eye". This proportion will be denoted as π_{ACT} within the runcaciguat treatment arm and as π_{PLC} within the Placebo treatment arm.

The study will be evaluated using a Bayesian approach with non-informative prior distribution. Using this approach for inference it is possible to base decisions directly on the posterior probabilities of the hypotheses of interest. Therefore, in a Bayesian setting it is not necessary to specify an alternative hypothesis.

The hypotheses of interest are the following:

- Hypothesis of clinical activity: $\pi_{ACT} > \pi_{PLC}$
- Hypothesis of clinical relevance: $\pi_{ACT} > 0.25$

09 FEB 2023 Page: 60 of 95

9.2 Sample size determination

The overall planned sample size is displayed in Table 9-1.

Table 9-1 Planned sample size

	Target dose	Part 1	Part 2	Total	
Randomized	Placebo	6	40	46	
	30 mg	-	-	-	
	60 mg	-	-	-	
	90 mg	-	-	-	
	120 mg	12	40	52	
	Overall	18	80	98	
Evaluable*				80	

^{*}minimum evaluable for primary endpoint

The relative contribution of Part 1 and Part 2 to the combined total of N = 98 randomized participants may vary. The assessment of the primary endpoint will include the combined total of all evaluable participants.

If unexpectedly high dropout rates occur (e.g. due to COVID-19), the number of randomized participants may be increased by up to 20%.

The study will use a Bayesian concept for inference, which is based on the posterior probabilities that the research hypotheses are true. Proof of concept shall be defined as fulfillment of the following criteria:

- \geq 90% posterior probability for the hypothesis of clinical activity (i.e. $Pr(\pi_{ACT} > \pi_{PLC} | data) \geq 0.9$)
- $\geq 50\%$ posterior probability for the hypothesis of clinical relevance (i.e. $Pr(\pi_{ACT} > 0.25 | data) \geq 0.5$).

The sample size has been chosen to provide at least 90% probability to obtain proof of concept.

The following assumptions have been used

- True response probability for placebo: 10%
- True response probability for runcaciguat 120 mg: 35%

The response criterion is assumed to be binomially distributed. For the Bayesian evaluation, a Jeffries' prior (i.e. a Beta (0.5;0.5)-prior) has been used. Sample size was determined with a simulation approach using the R environment.

To be able to declare both clinical activity and clinical relevance ≥ 40 evaluable patients are needed in both groups.

98 participants will be randomly assigned to the study intervention such that approximately 80 evaluable participants complete the study. Of 98 participants, 18 participants will be randomized with a ratio of 2:1 to highest runcaciguat dose and placebo for Part 1 (PK/PD). 80 participants will be randomized with a ratio of 1:1 to placebo and runcaciguat for Part 2 (Table 9-1).

09 FEB 2023 Page: 61 of 95

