To assess the efficacy, the retinal morphology will be investigated by 7-field color fundus photography (CFP) supported by 7 Field FA images for the assessment of the DRSS by a central reading center. Two-step DRSS improvement at 48 weeks of treatment will be the primary efficacy endpoint. Additional DRSS assessments are done after 12 and 24 weeks of treatment. In addition, vision-threatening complications will be recorded throughout the study and assessed as secondary efficacy endpoint.

During the course of the study, 16 visits are planned, including the screening visit (Visit 1) and the end-of-study visit (Visit 16). Visit intervals are weekly during the first 4 weeks, while the dose of runcaciguat (or placebo) is titrated to the target dose, then fortnightly for the next 4 weeks and then every 4 weeks up to Week 25 (Visit 12). The subsequent visits, up to end of treatment in Week 49 (Visit 15), will be at 8-week intervals. The end-of-study visit, Visit 16, will take place 4 weeks later.

Number of participants:

A combined total of approximately 98 participants for Part 1 and 2 will be randomly assigned for an estimated total of \geq 40 participants per intervention group evaluable for primary endpoint assessment, as defined in Section 9.2. The estimated screen failure rate is approximately 50%.

Intervention groups and duration:

Participants are randomly assigned to one of two study arms. Assignment will be masked, as detailed in Section 6.3. After providing informed consent, participants will be screened (Visit 1) and within up to 4 weeks, eligible participants will be randomized and treatment will be initiated at Visit 2. During the initial four weeks, treatment will be titrated to the target dose of 120 mg runcaciguat or matching placebo. Treatment will start at 30 mg runcaciguat or placebo once daily for the first week. If well tolerated, the dose will be increased to 60 mg runcaciguat or placebo at Visit 3 in the second week of treatment, then to 90 mg runcaciguat or placebo at Visit 4 in the third week of treatment, and finally to 120 mg runcaciguat or placebo at Visit 5.

In case of intolerability (see Section 6.5.1) treatment may continue without up-titration or the dose may be reduced by one titration step.

Treatment will continue at the highest tolerated dose until completion of 48 weeks of treatment if tolerated, or until development of a vision threatening complication or development of PDR.

[figure not shown]

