2.1 Study rationale

The clinical development of runcaciguat so far has shown that the compound is well tolerated. However, formulation challenges lead to an inconvenient dosing regimen and a difficult to manage supply chain.

The Sponsor plans to run the NEON-NPDR study with runcaciguat as a PoC trial for sGC activators in NPDR. Although the sGC activator runcaciguat will not be further developed, the results from this trial will generate a general PoC for sGC activation in NPDR using a investigational compound that has proven its activity in nonclinical and in phase 1 clinical trials and that has been shown to be well tolerated.

In addition, detailed pharmacokinetic and pharmacodynamic assessments will be performed on a subset of participants enrolled in Part 1. The resulting improved PK/PD understanding will facilitate the translation of the results obtained with the runcaciguat to other sGC activators.

Therefore, this trial will be the basis for a general decision on the suitability of sGC activators for treatment of NPDR. In the positive case, this may optimize the development of subsequent sGC activators. In particular the data will facilitate the choice of the appropriate dose-range and the choice of the most appropriate treatment duration. This knowledge will result in safer and more focused clinical trials with the follow-up compound.

09 FEB 2023 Page: 18 of 95

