9.4.2 Primary endpoint

The primary endpoint is "≥ 2-step improvement in DRSS at 48 weeks of treatment in the study eye".

Missing data for this endpoint will be imputed using the last measured DRSS score prior to this

If the last measured DRSS score already showed an improvement by ≥ 2 steps at the last measurement prior to the missing assessment, the participant will be considered a responder for the primary endpoint. Otherwise, the participant will be considered a non-responder.

Participants that had a vision-threatening complication as defined in Section 8.1.2 prior to the missing assessment will be considered non-responders.

The primary analysis will be conducted using a Bayesian framework. This decision depends upon the following criteria:

- (a) there is \geq 90% posterior probability for superiority vs placebo and
- (b) if there is \geq 50% posterior probability that the proportion of patients with DRSS \geq 2-step improvement exceeds 25%.

The response criterion is assumed to be binomially distributed within each treatment arm. For the Bayesian evaluation, a Jeffries' prior (i.e. a Beta (0.5;0.5)-prior) will be used. Under these assumptions, the posterior distribution for the parameter π will be a Beta (k+0.5,n-k+0.5)-distribution, where

- k is the number of patients with DRSS \geq 2step improvement within the respective study arm and
- n is the number of participants within the respective study arms.

In order to demonstrate criterion (a), the posterior distribution of $\pi_{ACT} - \pi_{PLC}$ will be used to establish the posterior probability that $\pi_{ACT} - \pi_{PLC} > 0$ (e.g. by using a Monte-Carloapproach).

The posterior distribution for criterion (b) can be directly evaluated from the Beta (k+0.5,n-k+0.5)- distribution in the runcaciguat arm.

This primary analysis will be conducted on the PPS. A sensitivity analysis will be performed on the FAS. Further sensitivity analyses will include a separate analysis for each runcaciguat dose level that was reached during titration (on the PPS), as well as an analysis in the subpopulation of participants without major changes in vital signs (i.e. systolic blood pressure and pulse rate). Another sensitivity analysis will be conducted using multiple imputations for missing data. This analysis will be described in the SAP in a more detailed way.

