### 5. Sample Size Determination

For the evaluation, a Bayesian concept for inference will be used, which is based on the posterior probabilities that the research hypotheses are true. Clinically relevant benefit of runcaciguat in treatment of advanced NPDR will be considered established and will result in "PoC" if the following criteria are met:

- $\geq$  90% posterior probability for the hypothesis of clinical activity (i.e.,  $P(\pi_{ACT} > \pi_{PLC} | data) \geq 0.9$ )
- $\geq 50\%$  posterior probability for the hypothesis of clinical relevance (i.e.,  $P(\pi_{ACT} > 0.25 | data) \geq 0.5$ ).

The sample size has been chosen to provide at least 90% probability to obtain PoC under the following assumptions:

- True response probability for placebo: 10%
- True response probability for runcaciguat 120 mg: 35%

The response criterion is assumed to be binomially distributed. For the Bayesian evaluation, a Jeffries' prior (i.e., a Beta (0.5;0.5)-prior) has been used. Sample size was determined with a simulation approach using the R environment.

CONFIDENTIAL	Statistical Analysis Plan BAY 1101042 / 20739	
	Version 3.0	Page: 32 of 35

To be able to declare both clinical activity and clinical relevance  $\geq 40$  evaluable participants are needed in both groups.

98 participants will be randomly assigned to the study intervention such that approximately 80 evaluable participants complete the study. Of 98 participants, 18 participants will be randomized with a ratio of 2:1 to highest runcaciguat dose and placebo for Part 1. 80 participants will be randomized with a ratio of 1:1 to placebo and runcaciguat for Part 2 (Table 5-1).

Table 5-1: Planned sample size

	Target dose	Part 1	Part 2	Total
Randomized	Placebo	6	40	46
	30 mg	-	-	-
	60 mg	-	-	-
	90 mg	-	-	-
	120 mg	12	40	52
	Overall	18	80	98
Evaluable*				80

\*Minimum evaluable for primary endpoint.

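### The stated 90% probability of proof of concept is met at 40/40 evaluable, but 52:46 randomisation with 80 evaluable gives about 42/38 under equal loss, where it is 88.7%

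*Protocol*

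**What the plan says.** Protocol 9.2 declares proof of concept (PoC) when two posterior statements hold: at least 90% probability that the runcaciguat response rate exceeds placebo (activity), and at least 50% probability that the runcaciguat rate exceeds 25% (relevance). It assumes true rates of 35% and 10%, uses a Beta(0.5, 0.5) prior in each arm, and states: "The sample size has been chosen to provide at least 90% probability to obtain proof of concept". SAP 5 makes the same claim: "The sample size has been chosen to provide at least 90% probability to obtain PoC under the following assumptions".

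The per-arm condition in Protocol 9.2 is that at least 40 "evaluable patients are needed in both groups". The Synopsis also gives at least 40 "participants per intervention group evaluable for primary endpoint assessment, as defined in Section 9.2"; Section 9.2 gives numbers but no definition of evaluable.

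On total size, SAP 5 says "98 participants will be randomly assigned to the study intervention such that approximately 80 evaluable participants complete the study". Protocol Table 9-1 and SAP Table 5-1 show 52 randomised to runcaciguat (12 in Part 1, 40 in Part 2) and 46 to placebo (6 and 40). They mark 80 as the minimum evaluable, without a split by arm. Protocol 9.2 adds: "The relative contribution of Part 1 and Part 2 to the combined total of N = 98 randomized participants may vary".

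On dropout, Protocol 9.4.2 says: "Missing data for this endpoint will be imputed using the last measured DRSS score prior to this". SAP 4.2.2 scores dropout before Week 12, or a study-eye vision-threatening complication before the missing assessment, as non-response. It carries the last DRSS assessment forward for later dropout and restricts the primary analysis to compliant participants in the per protocol set.

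**The concern.** Four planning statements are made together: 52:46 randomised, a minimum of 80 evaluable, at least 40 evaluable in each group, and at least 90% probability of PoC. At 80 evaluable, 40 in each group is possible only at exactly 40/40. Starting from 52:46, that needs clearly higher loss on runcaciguat than on placebo, and no such assumption is written down. If loss is proportional, placebo falls below 40 and the stated probability is not reached.

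Protocol 2.1 says "this trial will be the basis for a general decision on the suitability of sGC activators" for NPDR, and at least 90% is the only stated chance of success. A negative result will be read against that figure, so it should be the figure for the allocation actually planned.

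**Working it through.** **Inputs.** Decision rule, prior, rates, allocation and sizes are from Protocol 9.2 and SAP 5. Loss by arm is not given in either document, so equal proportional loss is an assumption.

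**Method.** For arm sizes nA and nP, take every pair of responder counts, with kA ~ Binomial(nA, 0.35) and kP ~ Binomial(nP, 0.10). The posteriors are Beta(k + 0.5, n − k + 0.5). Sum the probability of all pairs for which P(πACT > πPLC | data) ≥ 0.9 and P(πACT > 0.25 | data) ≥ 0.5. This was done by exact enumeration with numerical integration.

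**Step 1: the plan's own figure.** At 40/40 the activity criterion alone is met with probability 93.6%, the relevance criterion alone with 93.6%, and both with **90.3%**. The claim reproduces. A simulation of 200,000 trials gave 90.4%.

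**Step 2: the split implied by 52:46.**
- Overall loss: 18/98 = 18.4%.
- Equal proportional loss: 52 × 80/98 = 42.4 and 46 × 80/98 = 37.6, so about 42/38.
- To reach 40/40 instead: 12/52 = 23.1% lost on runcaciguat and 6/46 = 13.0% on placebo.

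The mix of parts may also vary. With m participants in Part 1 (2:1) and 98 − m in Part 2 (1:1), the runcaciguat number at 80 evaluable is (2m/3 + (98 − m)/2) × 80/98:
- m = 0: 40.0/40.0
- m = 6: 40.8/39.2
- m = 12: 41.6/38.4
- m = 18: 42.4/37.6

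**Step 3: P(PoC) at 80 evaluable.**

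| Runcaciguat/placebo | P(PoC) |
|---|---|
| 40/40 | 90.3% |
| 41/39 | 86.8% |
| 42/38 | 88.7% (simulation 88.9%) |
| 43/37 | 89.5% |

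**Step 4: at least 40 in both arms.**

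| Runcaciguat/placebo | P(PoC) |
|---|---|
| 41/40 | 87.3% |
| 42/40 | 88.5% |
| 43/40 | 90.1% |
| 44/40 | 91.3% |
| 45/40 | 88.7% |
| 47/42 | 91.4% |
| 52/46 | 93.5% |

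Over all 91 combinations with 40 to 52 on runcaciguat and 40 to 46 on placebo, 66 reach 90% and 25 do not.

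**Why the figures go up and down.** The relevance criterion needs a whole number of responders. With 10 of 40, P(πACT > 0.25 | data) is 0.512 and passes. With 10 of 41 it is 0.476 and fails, so 11 are needed for 41 to 44 participants and 12 for 45 to 48. Each time the cut-off rises, the chance of meeting the relevance criterion drops (from 93.6% at 40 to 89.9% at 41) and then recovers as participants are added.

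**The case against.** The strongest reply is that nothing has been miscalculated. The 90% is tied to at least 40 evaluable in both groups, and it is correct at 40/40. A 42/38 split breaks that condition, so it is a different scenario, and it rests on an equal-loss assumption that the documents neither make nor exclude. It also needs all 18 losses to leave the analysis, whereas Protocol 9.4.2 and SAP 4.2.2 keep dropouts, carried forward or scored as non-responders; only validity findings and non-compliance remove participants. With dropouts kept, the analysed number exceeds 80, and at 52/46 the probability is 93.5%. The gap at 42/38 is 1.3 points and largely an effect of whole-number cut-offs.

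Most of this stands as a limit on the size of the point. It does not rescue the sentence as written. The plan gives 80 as the minimum evaluable, and its four statements agree at 80 only under unequal attrition that it does not mention. The per-arm condition does not secure 90% by itself, since 41/40, 42/40 and 45/40 all meet it and fall short.

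A reader might go further and infer that scoring dropouts as non-responders pulls the probability well below 90%. If 35% and 10% were rates before dropout scoring and an assumed 10% or 15% of each arm were then all non-responders, 52/46 would give 85.9% or 79.8%. The documents do not support that reading. Protocol 9.1 and SAP 2 define the two proportions as those meeting the primary endpoint, and Protocol 9.4.2 classifies participants with missing data as responders or non-responders for that endpoint. The natural reading is that 35% and 10% are rates for the endpoint as analysed. The dropout shares appear nowhere in the documents, and the calculation gives no credit to later dropouts whose carried-forward score is a response. What remains is missing detail: neither sample size section says so explicitly.

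**Conclusion.** The point holds as a small inconsistency between the stated probability and the planned allocation. At 80 evaluable the probability of PoC is about 87% to 90% for splits from 40/40 to 43/37, and 88.7% at the 42/38 expected under equal proportional loss, where placebo also misses the required 40. The shortfall is about 1 to 3 points.

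It should not be read as showing that N = 98 is too small, or that 40/40 is the only size that works. Many larger sizes reach 90%, and if dropouts stay in under the primary rule and the assumed rates apply to the endpoint as analysed, the probability is 91.4% at 47/42 and 93.5% at 52/46. The conclusion rests on the plan's rates, prior and decision rule. The 42/38 figure also rests on equal proportional loss and on all 18 losses leaving the analysis.

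**What to change.** Keep N = 98, the decision rule, the target of at least 40 per arm and the option to randomise up to 20% more. In Protocol 9.2 and SAP 5:

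1. Replace the at-least-90% claim with: *about 87–90% at 80 evaluable, depending on the split by arm (88.7% at 42/38 under equal loss; 90.3% at 40/40), and 93.5% if all 98 are analysed*.
2. Give the expected evaluable number per arm (about 42 runcaciguat and 38 placebo under equal loss), and label the loss pattern as an assumption.
3. As a clarification, add one sentence that defines evaluable and says that 35% and 10% are rates under the primary estimand's scoring.

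Do not add scenarios with assumed dropout non-response shares; the documents give no basis for the shares.

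The cost is text only: no extra participants and no change to the analysis. The stated probability at 80 evaluable becomes slightly less favourable.
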